8.3 Sub-group analyses

The following subgroups analyses were specified in the original study protocol, but will only be conducted if there are at least 10 participants falling into the minority category at baseline. They will be severely underpowered so are exploratory and will mostly be informative for describing safety outcomes across subgroups. Statistical models will be run as in the primary analyses but with interaction terms fitted for these factors and p-values for interaction will be calculated.

- Gender (male/female)
- Ethnicity (white/non-white)
- Symptom severity at enrolment (PCFSS 3+ or <3).
- Symptom duration at enrolment (<1.5 years or 1.5+ years).

APPENDIX

This appendix contains dummy tables corresponding to the main analyses described in the SAP. The exact format and presentation of the tables may vary in the final reports.

Appendix Table 1: Dummy table for baseline description of study participants, APRIL Trial.

Baseline characteristic		Intervention	Control arm
Age – mean (SD)		arm (N=)	(N=)
Gender – N (%			
	%) White British		
Education – N	I (%) completed university		
Work status –	N (%) in work		
Current smok	er – N (%)		
Co-	Diabetes – N (%)		
morbidities	Hypertension – N (%)		
	Lung condition – N (%)		
	Other – N (%)		
Duration of	<3 months - N (%)		
Long COVID	3-12 months - N (%)		
	12+ months - N (%)		
PCFSS at	1 – negligible limitations		
baseline	2 – occasional limitations		
	3 – some limitations		
	4 – severe limitations		
Quality of life by PROMIS 29+1 at baseline – mean (SD)			
Quality of life by EQ-VAS at baseline – mean (SD)			
Symptom burden (count) at baseline – mean (SD)			

SD is standard deviation. PCFSS is post-COVID functional status scale.

Appendix Table 2: Dummy table for medication and protocol adherence among those initiating a given month medication (i.e. if someone withdrew half-way through month 2, they would be counted in the month 2 column but not month 3)

Medication and protocol adherence	Intervention arm (N=)		(N=)	Control arm (N=)		
	M1	M2	МЗ	M1	M2	M3
N participants on medication at start						
Mean % monthly tablets taken (SD)						
Mean days after end of month that						
patient survey was completed (SD)						
Mean days after end of month that						
clinical monitoring was completed (SD)						

Appendix Table 3: Dummy table for primary and secondary patient-reported outcome analyses

	Outcome at 3-months		Effect size (95% CI)	P-value
	Intervention	Control arm	for intervention vs	
	arm (N=)	(N=)	control*	
Primary outcome: PCFSS (N and %)	*			•
0 – no limitations				
1 – negligible limitations				
2 – occasional limitations				
3 – some limitations				
4 – severe limitations				
Key secondary outcomes (mean and	SD)			•
Quality of life by PROMIS 29+2				
summary score				
Quality of life by EuroQol Visual				
Analogue Scale (0-100)				
Secondary outcomes (mean and SD	or N and %)			
Fatigue (PROMIS score)				
Sleep disturbance (PROMIS score)				
Anxiety (PROMIS score)				
Depression (PROMIS score)				
Social participation (PROMIS score)				
Physical function (PROMIS score)				
Cognitive function (PROMIS score)				
Pain interference (PROMIS score)				
Pain intensity				
Breathlessness♦				
Health utility (EQ-5D-5L)				
Missed work●				
Work productivity				
Symptom burden◆				
Symptom 1 (TBC) ●				
Symptom 2 (TBC) ●				
Symptom 3 (TBC) ●				

^{*}Adjusted for baseline level of outcome. Effect sizes represent mean difference in outcome score between intervention and control arms unless otherwise specified: ♦ = Odds ratio from ordinal logistic regression, • = Odds ratio from binary logistic regression.

Appendix Table 4: Dummy table for tabulation of safety outcomes

Safety outcome	Number of occurrences while on		Comment
	treatment		
	Intervention	Control arm	
	arm (N=)	(N=)	
Total person-months in study			
Suspected unexpected serious			
adverse reaction (SUSAR)			
Serious adverse event			
Pregnancy (participant or			
participant's partner)			
Adverse reaction involving LFT			
Other adverse reaction			
Adverse event involving LFT			
Other adverse event			

LFT is liver function test. Study definitions of SUSAR, serious adverse event, adverse reaction and adverse event are provided in the APRIL Trial protocol (V4.1).

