3.4 Study Assessments

3.4.1. Trial outcomes

Primary outcome measure

Self-reported functional status measured using the Post-COVID-19 Functional Status Scale (PCFS), at 3 months². Functional status is a key patient-centred indicator which measures the extent to which a condition limits a person's ability to conduct their usual activities. The PCFS has gained widespread popularity as a tool for measuring self-assessed functional status in Long COVID in trials and observational studies and has been translated into multiple languages. It was based on a similar, widely-used functional scale for stroke patients, and has been

validated in Long COVID patients³. The PCFS asks patients to consider a flow-chart of options that describe the extent of limitations to their daily activities over the past week. Based on the flow chart, they assign themselves to a grade between 0 (no functional limitations) to 4 (severe functional limitations).

Secondary outcome measures (all at 3 months)

- Quality of life by PROMIS 29+2 summary score,
- Self-reported fatigue, pain, sleep, anxiety, depression and social, physical and cognitive function by PROMIS 29+2 individual dimensions
- Self-reported breathlessness by modified MRC Dyspnoea Scale
- Health utility by EQ 5D-5L utility score
- Work status and productivity
- Other self-reported symptoms

Outcomes domains were selected to cover the most relevant key indicators for patients and policy makers as well as the most common symptoms of Long COVID. Outcome questionnaire instruments were chosen following thorough review of the literature and other ongoing studies, on the basis of wide use/validation, short length (to reduce participant burden), and relevance for this study population (ideally used successfully in Long COVID patients before). For outcome scores that required derivation, the approach used in the primary publication will be applied (PROMIS scores⁴ and EQ 5D-5L utility score⁵ using the most recent UK-based value set).

Safety outcomes

- SUSARs
- Severe adverse events (including pregnancies)
- All adverse events
- Adverse events related to liver function abnormalities
- Liver function test parameters

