3.4.3 Clinical monitoring

The investigator's clinical team assessed all participants at least monthly and conducted symptom-guided assessment as described in NICE Long Covid guidelines. Assessments took place at end of 30 days (±3 days, 1st interim assessment), 60 days (±3 days, 2nd interim assessment) and 91 days (final end of trial assessment) since treatment initiation. At each assessment, they actively elicited the participant's history related to a) any worsening of their Long covid, b) exacerbation of any other pre-existing conditions, and c) any side effects that might be related to the drug (including AE/SAE assessment if applicable). To guide assessment of c), we provided the clinical teams with full list of possible of side effects that have been observed for the trial product (regardless of whether causally attributed). Monthly assessments were conducted remotely or in-person, as per preference of the investigator or participant. Following the initial assessment, further in-person follow-up including any indicated tests and investigations were sought if needed based on participant's symptom assessment, and as guided by relevant local and national guidelines. In particular we highlighted the following areas of assessment: cardiac chest pain, symptoms suggestive of liver or kidney problems, and worsening of psychiatric symptoms.

In addition to these monthly clinical assessments, liver function tests (AST, ALT and bilirubin) were conducted at 30 days (i.e., along with first interim clinical monitoring assessment) and 91 days (i.e., at the end of trial assessment). The test at 30 days was intended to check for any early acute liver toxicity associated with the trial medication, while the test at 91 days was intended to assess for any longer-term effects associated with cumulative build-up of the product in the system. Additional liver function tests could be ordered by the study investigator at any point as deemed clinically indicated for the patient. All WOCBP had to complete an urine pregnancy test monthly during the trial. These tests were done after completing 1st and 2nd month of trial treatment, and after completing 3rd month's treatment at the final end of study assessment, to confirm that no pregnancies occurred during the trial treatment phase.

4 Statistical Analysis approach

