4.4.2 Per protocol

Additional analyses on a per-protocol basis will also be conducted, in which participants will be stratified into groups in terms of whether they took the trial treatment or not. The following groups will be analysed:

- Adherers: People who took at least 50% of the intended dose of treatment for at least 60 days (2 months) out of the total 90 days of treatment.
- Non-adherers: All others.

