Dummy table illustrating the presentation of the primary and secondary analysis results is given in appendix table 3.

7 Evaluation of safety outcomes

A table will be presented with counts of the following adverse safety outcomes, by trial arm (appendix table 4):

- SUSAR
- Serious adverse event (SAE)
- Pregnancy
- Adverse reactions involving abnormal liver test results (adverse event designated as probably or definitely related to trial medication)
- All other adverse reactions
- Adverse events (designated possible or unlikely related to trial medication) involving abnormal liver test results
- All other adverse events (designated possible or unlikely related to trial medication)

Further description and discussion of any SUSAR, SAE, pregnancy, adverse reactions and abnormal liver test results will be provided in the text (as the numbers of these are anticipated to be few). For each abnormal liver test result, the status of liver function at baseline will be mentioned, as abnormal liver function at baseline is expected to be linked to abnormal results during follow-up (although numbers are expected to be too small to formally test this). All adverse events will be broken down into specific categories (e.g. headache, nausea, etc) by trial arm in an appendix table. We will also present adverse events by trial arm stratified by gender in the same appendix table.

Changes over time in liver function test (LFT) results by arm will be described through data visualisation. Specifically, we will plot the mean and standard error values of AST, ALT and bilirubin at baseline, month 1 and month 3 by trial arm. T-test for the differences in each LFT will be calculated at each timepoint, crudely and with adjustment for baseline level. The corresponding numerical results will be given in an appendix table.

8 Additional analyses

The following additional analyses will only be applied to primary and key secondary to avoid multiplicity of analysis results. Apart from the specific aspects mentioned, each analysis will be the same as described in section 6.

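### Appendix Table 4 counts events on treatment but shows exposure in study, section 7 gives the same table no such limit, and the status of day-91 liver findings is left open

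*SAP*

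**What the plan says.** Appendix Table 4 is the shell for the safety results. Its two count columns are headed "Number of occurrences while on" treatment, and its single exposure row is "Total person-months in study". No lag after the last dose is given.

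Section 7 introduces the same table differently: "A table will be presented with counts of the following adverse safety outcomes, by trial arm (appendix table 4"). That text carries no on-treatment limit and mentions no rate.

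Three other places bear on the window:

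- Section 4.4.2 fixes the course length when it defines adherers as people who took enough treatment "for at least 60 days (2 months) out of the total 90 days of treatment".
- Section 3.4.3 says that liver function tests "were conducted at 30 days (i.e., along with first interim clinical monitoring assessment) and 91 days (i.e., at the end of trial assessment"), and that "the test at 91 days was intended to assess for any longer-term effects associated with cumulative build-up of the product in the system".
- Section 4.5 distinguishes complete withdrawals, who stop both medication and questionnaires, from partial withdrawals, who stop medication but go on completing questionnaires.

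Section 3.4.1 lists "All adverse events" among the safety outcomes. Section 3.2 says that the emphasis of the report will fall on safety.

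**The concern.** A count and the person-time beside it should run on the same clock. Here the count stops when treatment stops, while the person-time runs on for anyone who remains in follow-up off drug. A participant who stops at month 1 and continues to month 3 would contribute three person-months, but none of the events of the last two.

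The body text and the shell also disagree on which events belong in the table, so two analysts could fill it differently from the same data. The final liver test sits one day beyond the planned course, and without a stated window its findings may be counted or not at the analyst's choice.

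This matters more than usual because the trial stopped at 105 participants, the SAP expects the primary analysis to be underpowered, and it presents safety as the informative part. If stopping is related to harm, events after stopping are among those a reader most wants to see.

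**Working it through.** The SAP states no safety rate, person-time or discontinuation figure, so there is no figure of its own to reproduce. The check has two parts.

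**Which events count**

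- Section 7: counts by arm, no restriction by treatment status.
- Appendix Table 4: counts restricted to time on treatment, no lag.
- Course length 90 days (section 4.4.2); liver tests at days 30 and 91 (section 3.4.3). For someone who finishes on schedule, the second of the two scheduled post-baseline tests falls 91 − 90 = 1 day after the course ends. Whether an abnormality first found then occurred while on treatment is not defined.
- Section 4.5: partial withdrawals create study time off treatment. Their events in that time fit section 7 but not the table heading.

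**What the mixed clocks would do to a rate**

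Assumptions, none of them in the documents: three planned months; stoppers stop at the end of month 1; a share *f* of them stays in study to month 3 and the rest leave at once; a constant true on-treatment event rate, equal in both arms. Let *d* be the proportion of an arm that stops.

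- On-treatment months per person = 3(1 − d) + d = 3 − 2d
- In-study months per person = 3(1 − d) + d[3f + (1 − f)] = 3 − 2d(1 − f)
- Recorded rate ÷ true on-treatment rate = (3 − 2d) ÷ (3 − 2d(1 − f))

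For d = 20% and f = 1: on treatment 0.8 × 3 + 0.2 × 1 = 2.6; in study 3.0; 2.6 ÷ 3.0 = 0.867, an understatement of 13%.

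Recorded rate as a fraction of the true rate:

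| Stopping (d) | All stay (f = 1) | Half stay (f = 0.5) | None stay (f = 0) |
|---|---|---|---|
| 10% | 2.8/3.0 = 0.933 | 2.8/2.9 = 0.966 | 1.00 |
| 20% | 2.6/3.0 = 0.867 | 2.6/2.8 = 0.929 | 1.00 |
| 30% | 2.4/3.0 = 0.800 | 2.4/2.7 = 0.889 | 1.00 |
| 40% | 2.2/3.0 = 0.733 | 2.2/2.6 = 0.846 | 1.00 |

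Apparent rate ratio against an arm with 10% stopping, when the true ratio is 1.00:

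| Stopping in the other arm | All stay | Half stay | None stay |
|---|---|---|---|
| 10% | 1.00 | 1.00 | 1.00 |
| 20% | 0.93 | 0.96 | 1.00 |
| 30% | 0.86 | 0.92 | 1.00 |
| 40% | 0.79 | 0.88 | 1.00 |

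With on-treatment events over on-treatment months, the ratio is 1.00 in every cell. Arm size and the level of the true rate cancel. The number of post-stopping events left out cannot be calculated from the documents.

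**The case against.** The strongest reply is that the defect lies in one heading of a dummy table. The SAP promises counts, not rates; person-months is a row on display, and no text makes it a denominator. The appendix says that table format may vary. Complete withdrawals add little or no off-treatment study time, and the event that leads someone to stop normally begins on treatment and would be counted. All of this stands and limits the size of the point. It does not remove it: which events are counted is a definition rather than a matter of format, and a person-months row placed over event counts invites the division.

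A reader might infer that the table excludes the day-91 liver test, so that late liver harm is lost. The documents do not support that. The heading limits occurrences, not dates of detection, and section 3.4.3 uses the end-of-study pregnancy test to confirm what happened during the treatment phase, so a day-91 finding could fairly be counted. Section 7 also plans narrative on abnormal liver results with baseline status, AST, ALT and bilirubin at baseline, month 1 and month 3 by arm with between-arm tests, and a breakdown of all adverse events by arm. None of these is tied to time on treatment.

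A reader might also infer that events judged unrelated have no place, because section 7 words its last row as "All other adverse events (designated possible or unlikely related to trial medication"). The matching row in Table 4 carries no such limit, and the causality scale is left to the protocol, which is not at hand.

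**Conclusion.** The point holds in a limited form. Table 4 and section 7 disagree on which events are counted, the count and the exposure in Table 4 run on different clocks, and the place of day-91 findings is undefined. Followed literally, the table omits events after early stopping.

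The effect on any rate is conditional. It needs stoppers who remain in study, and it distorts the comparison only if off-treatment study time differs between arms. Under the assumptions shown, the understatement at 20% stopping runs from zero (none stay) to 13% (all stay). A reader might take from this that the table favours the arm with more stopping. That follows only if those who stop also stay in follow-up, and the SAP gives no figures on either.

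The gap is in the main safety table and not in the safety report as a whole. It is still worth closing before the code is broken, because the SAP rests its value on safety and the choice of window should not be made with the data in view.

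**What to change.** In section 7 and in the heading of Appendix Table 4, define one safety window: from first dose to the end-of-trial assessment, including the day-91 liver test, or to last contact if earlier, regardless of treatment status. Compute person-months over that same window. If an on-treatment version is also wanted, give it as a supplement with on-treatment person-months and a stated lag.

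Preferably, though not essential to the point, show participants with at least one event as n/N (%) beside the number of events, and add total rows for any adverse event and any liver-related adverse event.

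The cost is a few lines of text and a small change to the table shell. One limit should be stated with the results: section 4.5 says that partial withdrawals continued questionnaires but does not mention their clinical monitoring, so off-treatment events may be less completely recorded.
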